Clinical data will include information on decayed, missing and filled teeth (DMFT). This data will only be collected at T0, as it is not possible to observe any change during the follow-up period. Moreover, we will collect clinical data on plaque and mucosal inflammation, using the MPS index. This is our main variable of interest. Plaque is affected by oral hygiene routines and the intake of drinks and food that can damage teeth, and thus any observed difference in changes in plaque between the treatment group and the control group may be interpreted as an effect of the intervention. Dental staff has undergone a calibration exercise of both DMFT and MPS.

The questionnaire is extensive. It starts with some background questions about demographic and socio-economic status, which are not likely to change during the follow-up period, and thus only asked at T0. Next, we ask questions about their views on their own oral health. In particular, we ask them about how they perceive the condition of their own oral health, whether they want to improve it, whether they regularly visit a dentist outside of prison, their cleaning routines and their intake of food and drinks. Some of these questions are secondary variables of interest. In the case of an intervention effect, prisoners may have an adjusted view on their oral health, and they may change their oral cleaning routines and intake of food and drinks. We also ask them standardized questionnaires about their oral-health quality of life (OHIP-14) and their self-reported anxiety and discomfort to dental treatment (Corah). As these are unlikely to change during the follow-up period, they are only asked at T0.

We also collect data on their general physical and mental health. To measure mental health, we use the standardized questionnaire Mental Health Inventory 5 (MHI-5). We conduct the MHI-5 questionnaire at all meeting points, T0, T1 and T2, as we expect reduced effects of the intervention if they are experiencing worsened mental health. This may be important when studying heterogeneous effects of the intervention. Lastly, we collect data on their alcohol and drug use (outside of prison), using the short versions of alcohol use disorders identification test (AUDIT-4) and the drug use disorders identification test (DUDIT), collected only at T0.

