To test the overall effects of the intervention on our primary and secondary outcome variables, we will conduct non-parametric Wilcoxon Mann-Whitney U-tests. Given the ordinal outcome variables, we consider this test as more appropriate alternative relative to traditional two independent sample t-tests. We will compare the means of the treatment group and the control group at T0, T1 and T2. At T0 we expect no differences in means as no intervention has occurred. At T1 and T2 we expect better scores for the treatment group relative to the control group. Notably, our primary interest will be the difference in means at T1, as we expect more missing data at T2 due to prisoners being released from prison. However, for the intervention to have a long-lasting improvement on the prisoner's oral health, it is important that the intervention successfully enables the prisoner to make lasting changes. If we do not find a statistical difference between the treatment and the control group at T2, however, it may be hard to tell whether this is due to the intervention effect fading out or lack of power. See power analysis for more details on this, in which we show effect sizes possible to detect at different number of observations, given that power is set to 0.8 and number of sites is set to 4. As drop-out increases at T2, the higher the effect size must be for us to be able to detect any statistical difference between the groups.

Moreover, we are going to run multiple ordinal logistic regressions where we include selected covariates (see below). Running regressions allow us to control for the baseline measures of plaque

by using the baseline score of the outcome variables as a lagged dependent variable, in addition to including other covariates likely to correlate with the treatment and to explain variation in the dependent variable. For robustness purposes we also run regressions with fixed effects, controlling for unobserved individual time-invariant characteristics.

Covariates:

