The main covariate included in the analysis is the pre-intervention MPS index score. For our secondary outcome variables, the equivalent pre-treatment observation is used as covariate to control for pre-intervention status. We include these as they are likely to explain a lot of the variation in the outcome variable. Furthermore, we include a dummy variable for each prison, to control for prison-specific variation, and a dummy variable for the person who completed the MI-intervention with the prisoner.

As described below, we will also conduct heterogeneous analysis. Covariates that are relevant for such analysis (HASI and depressive symptoms) will also be included in the overall analysis.

Other covariates may be included, however given that we have successfully randomized prisoners, they should not affect our results. For robustness purposes, we will run analysis that include individual-specific covariates such as age, education, and length of prison sentence.

Heterogeneous analysis:

We will study heterogeneous effects of the intervention depending on their baseline score of the primary outcome variable. Those who score high on level of plaque have the greatest improvement potential. However, they might also be those with the least interest in taking care of their oral health. As motivational interviewing is designed to also motivate those who are not motivated, they may still experience the greatest improvement from the intervention.

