Moreover, we will study heterogeneous effects of the intervention depending on the prisoner's score on the learning ability screening test (HASI). The minimum and maximum score on the screening test is 45,7 and 96,4 points, respectively. HASI suggests that the border line of 85 should be used to indicate possible intellectual disabilities. However, when Søndena et al. (2008) validated the Norwegian translated version of the test on a sample of prisoners in the Norwegian Correctional Service, they found that this cut off provided many false positive cases compared to the more comprehensive Wechsler Abbreviated Scale of Intelligence (WASI). They suggested a lower cut off score of 80 to avoid too many false positives. We will study heterogeneous effects using both these cut offs in separate regressions, constructing dummy variables that separate those below or above the cut off, and interact these dummy variables with the treatment variable. There are two main reasons why we might expect (or not expect) a heterogeneous effect of the intervention for these groups. Motivational interviewing is developed to help patient groups that do not respond to traditional therapy, suggesting that prisoners with possible intellectual disabilities may still benefit from the intervention. On the other hand, however, scoring low on the ability screening may make it more difficult to benefit from the from the MI-based conversation and to use it as a basis for change.

Finally, we are going to study heterogeneous effects of the intervention depending on the prisoner's depressive symptoms, measured by MHI-5. We expect those with stronger depressive symptoms to respond less to the intervention, as they are less likely to be in a state where they prioritize their oral health and to benefit from the MI-based conversation. We collect MHI-5 at both T0, T1 and T2. As MHI-5 at T1 and T2 may be correlated with the intervention, we must use MHI-5 measured at T0 as

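### Extra covariates in the adjusted regressions are justified by correlation with treatment, which is the wrong criterion in a randomised trial; require T0 measurement and prognostic value instead

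*Combined protocol and SAP*

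**What the plan says.** Under Statistical model specification, the first analysis is unadjusted: "To test the overall effects of the intervention on our primary and secondary outcome variables, we will conduct non-parametric Wilcoxon Mann-Whitney U-tests". The plan then adds adjusted models: "we are going to run multiple ordinal logistic regressions where we include selected covariates (see below". These control for the baseline score of the outcome, "including other covariates likely to correlate with the treatment and to explain variation in the dependent variable".

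The Covariates section supplies the list. It starts with "The main covariate included in the analysis is the pre-intervention MPS index score", and for secondary outcomes with the matching pre-treatment answer. The reason given for these is prognostic: "We include these as they are likely to explain a lot of the variation in the outcome variable". It then names prison dummies, a dummy for whoever delivered the MI conversation, HASI and depressive symptoms. Age, education and sentence length are kept for robustness runs. The list is not closed: "Other covariates may be included, however given that we have successfully randomized prisoners, they should not affect our results".

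Under Heterogeneous analysis the plan takes the opposite view of correlation with treatment: "As MHI-5 at T1 and T2 may be correlated with the intervention, we must use MHI-5 measured at T0". It also describes a further analysis that controls for change in depressive symptoms, and itself labels that analysis endogenous.

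**The concern.** Looking for covariates related both to exposure and to outcome is how confounders are chosen in an observational study. Randomisation removes the need for the first condition and changes what it picks out. A variable recorded before the arm is known has no systematic relation to treatment. One that does have such a relation has either been moved by the intervention or is defined by allocation. Adding the second condition, that it predicts the outcome, does not screen such variables out: a variable moved by treatment and predictive of outcome is the description of a mediator. Conversely, a purely prognostic T0 variable, the right kind of covariate, fails the rule as written.

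At stake is the treatment coefficient in the adjusted regressions. If a variable of this kind enters, the coefficient no longer estimates the overall effect of the intervention but only the part that does not pass through that variable. With an open list and no T0 restriction, the plan's text does not prevent this.

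**Working it through.** **1. What can correlate with treatment.** The Blinding section says that the T0 examination and questionnaire are completed before the arm is revealed. With 1:1 allocation, the correlation r between a T0 covariate and treatment then has mean 0 and standard deviation of about 1/√N. At N = 320 this is 1/√320 = 0.056. A simulation gave 0.057, with 5.1% of draws nominally significant at the 5% level. That is chance and nothing more.

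**2. The named covariates, by timing.**

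| Covariate | When fixed | Systematic correlation with treatment? |
|---|---|---|
| Baseline score of the outcome | T0, before the arm is revealed | No, chance only |
| Prison | Blocking factor | No, balanced by design |
| Age, education, sentence length (robustness) | Before the intervention | No, chance only |
| Depressive symptoms (MHI-5) | Collected at T0, T1 and T2; time point not stated for the overall model | No at T0; possible at T1 or T2 |
| HASI | T1 (Project summary) | Possible, though probably small if it screens a stable ability |
| Person who delivered MI | Exists only for treated prisoners | Yes, by definition |

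Most entries are sound. The last one shows that the criterion has practical effect. The provider dummies add up to the treatment indicator, so a full set cannot be separated from treatment. With 6 providers (an assumed number), the design matrix with intercept and treatment has 8 columns but rank 7. If one provider is dropped as reference, the treatment coefficient becomes the effect for that provider only.

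**3. The statements side by side.** Statistical model specification makes correlation with treatment a reason to include a covariate. Heterogeneous analysis makes it the reason not to use later MHI-5. Covariates says that further covariates should not matter after randomisation, which is true of T0 variables but not of mediators. These cannot all be the rule.

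**4. The plan's figures used below.** Power calculations gives 106 prisoners for an effect of 0.5 and 320 for 0.286. Both reproduce with the Wilcoxon efficiency 3/π and a one-sided 5% test. For 320: effective n per arm = 160 × 3/π = 152.8; noncentrality = 0.286 × √(152.8/2) = 2.50; power 0.802. For 106: power 0.803. Two-sided testing would need 404 and 134; the plan does not state sidedness. The present point does not depend on this. Only 0.286, N = 320 and a baseline R² of about 0.5 (the plan expects 50% to 60%) are carried forward.

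**5. Hypothetical size.** In a linear model, let a share s of the total effect pass through a post-intervention covariate. Adjusting for it leaves (1 − s) × total effect:

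| s (assumed) | (1 − s) × 0.286 | Simulated estimate |
|---|---|---|
| 0% | 0.286 | 0.287 |
| 25% | 0.2145 | 0.214 |
| 50% | 0.143 | 0.144 |
| 75% | 0.0715 | 0.071 |
| 100% | 0 | −0.001 |

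Adjusting for the baseline score alone gave 0.284 to 0.287 throughout. A second simulation fixed the coefficient of the post-intervention covariate on the outcome at 0.4 (assumed) and that of the baseline score at 0.7. Two-sided power was about 94–95% with baseline adjustment only. With the extra covariate it fell to about 89%, 54% and 18% at s = 25%, 50% and 75%. Those cases require the intervention to shift the covariate by s × 0.286/0.4 = 0.18, 0.36 and 0.54 units, so the last is demanding.

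**The case against.** The strongest reply is that the phrase is a loose rationale, not an operating rule. The same paragraph sends the reader to the Covariates section, where the list is mostly pre-intervention and the baseline scores are justified as prognostic. The remark that further covariates should not affect results only makes sense for pre-intervention variables. The authors plainly understand post-treatment bias: they insist on T0 MHI-5 for the interaction analysis and caveat the analysis of MHI-5 change. All of this stands, and it keeps the point small. It does not remove it. The criterion is still the stated reason for adding covariates, the list it governs is open, and nothing confines additions to T0.

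A reader might infer more than the documents support:

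- *That the plan will adjust for T1 or T2 brushing and intake.* The plan does say "Plaque is affected by oral hygiene routines and the intake of drinks and food that can damage teeth", and H2 and H3 expect the intervention to change those behaviours. But no section proposes them as covariates. They are secondary outcomes, with their own pre-treatment values as covariates.
- *That covariates will be picked on observed imbalance.* The arms are compared at T0, but that comparison is nowhere tied to covariate choice.
- *That adjustment removes the effect.* It removes the part that runs through the covariate, and all of it only under full mediation.

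**Conclusion.** The point holds as a defect of wording in the adjusted analyses. Correlation with treatment is a wrong inclusion criterion in this design, it conflicts with the plan's own handling of MHI-5, and the open list gives it room to act. The unadjusted Wilcoxon tests, listed first for the overall effect, are untouched.

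The documents do not fix a size. The loss ranges from nothing to the whole coefficient as the mediated share goes from 0 to 100%, and the plan gives no share. The figures above also use a linear model where the plan specifies ordinal logistic regression, so they illustrate direction and scale only. The correction should be made before analysis; it does not put the main comparison in doubt.

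**What to change.** In Statistical model specification, delete correlation with treatment as a reason for inclusion and write instead: *other covariates measured at T0, before the arm is revealed, and chosen because they are expected to explain variation in the outcome*.

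In Covariates:

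- close the list before arms are linked to outcomes;
- state that depressive symptoms in the overall model means MHI-5 at T0;
- state that no variable measured after T0 or defined by allocation enters the main overall-effect model. This takes out T1 HASI and the dummy for the person who delivered MI.

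Analyses that use T1 HASI or change in MHI-5 stay in the plan, labelled as heterogeneity or exploratory analyses.

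The cost is a few sentences, with no change to data collection. The one downside is that the adjusted model may lose a little precision by leaving out T1 HASI.

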All prisoners in the study undergo an oral examination to establish a baseline (hereafter T0) of oral health and a comprehensive questionnaire to identify risk factors and their attitude towards their oral health and oral treatment. Norwegian speaking prisoners are then randomized into either a treatment or control group. In the treatment group, dental staff initiate a conversation with the prisoner based on techniques from MI. Both groups finally receive a toilet bag with basic equipment to regularly clean their teeth. After 4 weeks and 12 weeks (hereafter T1 and T2), prisoners are invited back for another oral examination and a follow-up questionnaire, to measure changes in oral hygiene, oral cleaning routines, and attitude towards their oral health. At T1 we also conduct a screening of general learning difficulties using the validated screening tool HASI (Hayes, 2002). If the intervention proves to be an effective tool in improving oral hygiene, oral cleaning routines, and/or attitude towards own oral health, it can serve as an alternative proactive approach to improve oral health of a vulnerable group in society. If the improvements in oral hygiene and oral cleaning routines are long lasting, this may in turn lead to a reduced need of oral treatment. An improved attitude towards own oral health may, together with other rehabilitation programs in prison, improve the prisoner's self-esteem and chances to successfully returning to society after having served their prison sentence.

Study Design

Hypothesis:

H1: The conversation based on Motivating Interviewing (hereby the intervention) leads to a reduction in observed plaque and gingival inflammation for prisoners.

H2: The intervention leads to improved reported cleaning routines of prisoners in general, and particularly brushing of teeth.

H3: The intervention leads to a reduction in prisoners' intake of food and drinks in total, and particularly in-between meals.

H4: The intervention leads to improved perceptions about the prisoner's oral health. It improves how they view their oral health, they consider their oral health as more important, they report an increased wish to improve it, and they have increased efforts to improve it.

H5: The intervention leads to an increase in number of questions the prisoner asks during their visit with the dental staff, suggesting an increase in curiosity concerning their oral health.

Treatment effects and measurements:

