The end date for data collection depends, in addition to uncertainty regarding whether additional funding is approved, on the extent that the ongoing pandemic will affect data collection. If stricter infection control measures are enforced, prisons are likely to quickly deny access for external partners. The new omicron variant of the corona virus has already forced delays in three out of four prisons. During a period in which we are not allowed to enter a prison, we will be forced to do follow-up examinations at times deviating from the times described above and our flow chart presented below. We are also likely to experience higher attrition during such periods, as prisoners are released or moved to a prison outside Rogaland County before we are allowed to do follow-up examinations. Such attrition is independent of treatment status. During periods we are not allowed to enter the prison, dental staff will work in their regular clinic instead. Therefore, we are not spending project resources during lockdowns.

During the data collection period we are aiming to recruit around 500 subjects. The number of subjects we can recruit depends on several factors. First, we rely on enough people serving their prison sentence during the data collection period. We know that prisons in Rogaland County have not been fully occupied in recent years. Second, the proportion of prisoners who choose to participate is uncertain. Third, time spent on each prisoner depends on how effectively the prison staff can bring prisoners to the examination room and how effective the routines of dental staff are. Forth, we do not know many of the prisoners have sufficient Norwegian language to participate in the study. See the power calculation section for a more detailed discussion about the required sample size.

[figure not shown]
Each prisoner is followed for 12 weeks in total, and we continuously recruit prisoners in the data collection period. The intervention occurs only at time T₀, and only for those randomized to the treatment group. During the first few months we recruit primarily those who are already imprisoned, and once all of them have been given the chance to participate, we start recruiting new prisoners.

Intervention

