The intervention is a conversation lasting up to 30 minutes with the prisoner about his or her oral health, based on Motivational Interviewing. The intervention is carried out by dental staff in prison. Prior to the start of data collection, dental staff has been trained by MI certified specialists from the Regional Alcohol and Drug Competence Center in Rogaland County. The training has consisted of three days of seminar with group work and discussions, a practice MI-conversation that has been recorded, transcribed, and graded by the MI-center in Bergen, and direct feedback on this practice conversation. In addition, they receive continuous guidance from a MI specialist at the Center for Alcohol and Drug Research at Stavanger University Hospital.

The MI conversation follows the methodology of MI closely. The first step is for the dental staff to ask open questions to the prisoner, for example “what cleaning routines do you have for your teeth?” or “what benefits could you get from brushing your teeth twice a day?”. The next step is to confirm to the prisoner what he or she is doing, for example “you are really trying hard to take good care of your teeth” or “you have managed to have good cleaning routines multiple times in the past”. The third step is called reflection. At this stage, dental staff tries to provide reflections on what the prisoner have said, for example by repeating what the prisoner have said or say the same using synonyms (simple reflection), by extracting the underlying opinion or feeling (complex reflection), or by illuminate both negative and positive sides of the situation (double sided reflection). The final step is to summarize the conversation. In addition, the intervention included a change plan, in which the prisoner and dental staff agrees on specific behavior that the prisoner should follow based on the MI conversation.

Include a flow chart:

Data collection and sources of data:

Data collection will be carried out by trained dental staff inside the prisons during the data collection period. Most data collected will be on individual (prisoner) level. Moreover, we will collect basic information about each of the four prisons in our study.

The source of data will be a combination of clinical information from the oral examination, answers from the questionnaire, and a few observations done by dental staff during the consultation.

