Prisoners are not informed whether they are in the treatment or control group and are therefore blind to treatment status. Dental staff are blind to prisoners' treatment status at the time of the first oral examination and questionnaire. The prisoner's treatment status is revealed just after this. Hence, dental staff collects all data prior to knowing the prisoner's treatment status, and only learn this when they start the MI-based conversation. When prisoners are back at T1 and T2 for follow-up oral examinations and questionnaires, dental staff might still remember whether the prisoner was treated or not. To partially account for potential bias in the oral examination (assessment of oral hygiene and inflammation in gingival), there are two independent assessments of this at T1 and T2. See pre-specification of analytical decisions for more on this.

Power calculations:

We have used GPower and Optimal Design to conduct power calculations.

GPower is used to calculate required sample size for simple comparison of means for the main variables of interest between the treatment and control group, without considering that data is collected at multiple sites. We choose the non-parametric Wilcoxon-Mann-Whitney test, set alpha to 0.05 and required power to 0.8. There is uncertainty concerning the effect size. Previous literature offers some guidance, however there are several important differences to our study. MI-interventions to change oral health have previously been tested on periodontist patients and patients with mental illness, populations that differ from ours. For our main variable of interest, level of plaque, these studies have found effect sizes ranging from 0.286 to 1.213¹. However, one should note that these studies have used different indexes to measure plaque, questioning the comparability of the effect sizes. Setting the power estimate to a moderate level in this range, to 0.5,

¹ An effect size of 0.286 was found after 12 weeks in Brand et al. (2012), whereas an effect size of 1.213 was found in Godard et al. (2011).

our required sample size is 106 prisoners. If we use a more conservative estimate and set it to the lowest effect size observed in the studies referred to above (0.286), the required sample size is 320.

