Optimal Design is used to calculate the Minimum Detectable Effect Size (MDES) given that we block on prison level. Here we choose the Multi-Site trials under Person Randomized Trials. We set alpha to 0.05 and required power to 0.8. As we block on prison, we set number of sites (J) to 4. There are great uncertainty concerning effect size variation, how much of the variation in the outcome that can be explained by the blocking variable, and how much of the variation in the outcome can be explained by the covariate variable. Thus, we present power calculations based on bounds of these values. We set the range of effect size variation from 0.0 (equivalent to the fixed-effects model) to 0.05. Furthermore, we assume that the blocking variable can explain 20% to 30% of the variation in the outcome. And finally, we use the pre-intervention MPS index score from the oral examination as a covariate, expected to explain 50% to 60% of the variation in the post-intervention MPS index score.

Given these boundaries, and assuming we can recruit 100 prisoners in each prison, the most optimistic scenario allows us to detect an effect size of about 0.15. On the other hand, should we end up in the other end of the boundaries, we are only able to detect an effect size of about 0.55. The calculation is very sensitive to changes in the effect size variation, and less sensitive to changes in how much variation the blocking variable and the covariate variable can explain. The number of prisoners recruited in each prison is also an uncertain number. The prisons differ in size and number of prisoners. We are likely to have more than 100 prisoners recruited in three out of four prisons. The smallest prison in the region has only 18 rooms. The calculations above have not considered the imbalance of prison size.

Pre-specification of analytical decisions

Statistical model specification:

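### The MI-provider dummy exists only in the treatment arm, so the adjusted ordinal regressions leave the treatment main effect unidentified or turn it into one provider's effect

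*Combined protocol and SAP*

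**What the plan says.** Under Statistical model specification, the overall effects are tested with unadjusted Wilcoxon-Mann-Whitney tests, with T1 of main interest. The plan then adds that "we are going to run multiple ordinal logistic regressions where we include selected covariates". The Covariates section lists these as the baseline score, a dummy for each prison, and "a dummy variable for the person who completed the MI-intervention with the prisoner". The Heterogeneous analysis section shows that the regressions also carry a separate treatment variable.

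The conversation is delivered in one arm only. The Project summary says "In the treatment group, dental staff initiate a conversation with the prisoner based on techniques from MI", and the Expected timeline section says that the intervention takes place at T0 "and only for those randomized to the treatment group". Under Intervention: "The intervention is carried out by dental staff in prison". The number of staff is not given.

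The plan does not say how the provider variable is coded for controls, which provider is the reference, or which coefficient or contrast is to be read as the treatment effect.

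**The concern.** A covariate that is defined only for treated prisoners cannot be adjusted for like one observed in both arms. It subdivides the treatment arm and therefore competes directly with the treatment indicator.

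The coefficient that a reader would take as the adjusted overall effect then depends on which provider the software omits, or on a choice made after the data are seen. The adjusted regressions matter because they carry the baseline and prison terms assumed in the minimum detectable effect size (MDES) calculation under Power calculations, where "we use the pre-intervention MPS index score from the oral examination as a covariate". If the treatment coefficient from the model as worded is the one tested, that precision is not achieved.

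**Working it through.** **Inputs from the plan.** Four prisons; 1:1 allocation in blocks of four within prison; MPS as the sum of two four-point scores, so 2 to 8, or 7 categories; conservative sample size 320; optimistic MDES about 0.15 (100 per prison).

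**Assumed, because the plan is silent.** K = 2, 4, 6 or 8 providers, near-equal caseloads, four equal prisons, and the provider effects used in the simulations.

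**The plan's figure.** Taking 320 as N, it reproduces exactly (effect size 0.286, power 0.8, Wilcoxon efficiency 3/π) with a one-sided alpha of 0.05. Two-sided it would be 404. The plan does not state sidedness, and nothing below depends on it. The MDES of 0.15 is taken as stated.

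**Step 1: rank.** Let T be the treatment indicator and D_k = 1 if provider k delivered the conversation, 0 for controls. Each treated prisoner has exactly one provider, so D_1 + … + D_K = T. With intercept, arm, baseline, three prison dummies and K provider dummies there are 6 + K columns, of rank 5 + K: 8/7, 10/9, 12/11 and 14/13 for K = 2, 4, 6 and 8. For K = 4, 6 and 8 a separate check gave the same counts, and for K = 8 also with staff fixed to prisons.

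**Step 2: standard error with one dummy dropped.** The treatment coefficient now compares the reference provider's n_ref prisoners with the controls. Leaving the other covariates aside,

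SE ratio = sqrt[(1/n_ref + 1/n_C) / (1/n_T + 1/n_C)].

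With n_T = n_C and n_ref = n_T/K this is sqrt[(K + 1)/2]. For K = 6, 160 treated do not divide evenly; with 28 under the reference provider it is sqrt[(1/28 + 1/160)/(2/160)] = 1.83.

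| Providers | Formula | Linear model | Proportional-odds simulation (N = 320, 400 trials) |
|---|---|---|---|
| 2 | 1.22 | 1.23 | 1.22 |
| 4 | 1.58 | 1.58 | 1.58 |
| 6 | 1.83 | 1.83 | 1.83 |
| 8 | 2.12 | 2.12 | 2.12 |

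If each provider works in one prison only, the comparison is confined to that prison (40 treated, 40 controls). One provider per prison: sqrt[(2/40)/(2/160)] = 2.0. Two per prison: sqrt[(1/20 + 1/40)/(2/160)] = 2.45.

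**Step 3: consequence for the MDES.** In the crossed layout the optimistic value becomes 0.15 × 1.22 = 0.18 to 0.15 × 2.12 = 0.32.

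**Step 4: dependence on the reference.** With assumed provider log-odds effects spread from -0.1 to -0.9 (mean -0.5), the treatment coefficient averaged -0.09 to -0.14 with the weakest provider as reference and -0.91 to -0.92 with the strongest. Without the dummies it averaged -0.48 to -0.51. A second simulation (N = 400, four providers at -0.1, -0.4, -0.7 and -1.0, 60 replicates) gave -0.02 and -1.02 (SE 0.29), against -0.53 (SE 0.18) without the dummies; Monte Carlo error of the first two means is about 0.04. With equal provider effects there is no bias, only the larger SE.

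**Step 5: what survives.** With γ_k the provider coefficients (zero for the reference) and caseload weights w_k = n_k/n_T, the contrast β_T + Σ w_k γ_k recovers the average effect, with SE ratio about 1.00. Treatment-by-subgroup interaction terms have ratio 1.00 to 1.01 (linear model, 30% subgroup assumed). The treatment main effect in those interaction models has ratios 1.16, 1.43, 1.63 and 1.86, so within-subgroup effects would be distorted if they carry the same covariates.

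**The case against.** The strongest reply is that the authors mean the staff member who carried out the T0 visit. The Blinding section says staff collect all T0 data before allocation is revealed "and only learn this when they start the MI-based conversation", which suggests that the examiner also delivers the conversation. The scoring rule under Other issues refers to the original examiner without distinguishing arms, so this person is probably known for controls. On that reading treatment is identified and the SE ratio is 1.00. The reading is plausible, but the Covariates section names the person who completed the MI-intervention, and following it literally produces the defect.

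Other points stand and limit the scope:
- The main Wilcoxon-Mann-Whitney comparisons do not use this covariate.
- No information on the average effect is lost, because the weighted contrast recovers it. The plan does not specify that contrast.
- A singular matrix or a missing control arm would be noticed. Dropping one dummy, which software may do by itself, would not necessarily be.
- The bias figures rest on an invented spread of provider effects. The MDES figures scale only the optimistic end (zero effect-size variation); the multiplier should not be carried to the 0.55 end, where that variation matters greatly.
- The individual fixed-effects models absorb a time-invariant provider dummy. If it were coded to change after T0, the collinearity would return there too; the plan does not suggest that coding.

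**Conclusion.** The concern holds and should be fixed. The rank deficiency is exact and needs no assumption beyond ordinary dummy coding with controls set to 0. With one dummy dropped, the treatment coefficient estimates the reference provider's effect, with an SE about 1.2 to 2.1 times that without the dummies for 2 to 8 crossed providers, and 2.0 to 2.45 with staff fixed to prisons (4 and 8 providers). Any bias depends on how far providers differ, which is unknown.

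What is affected is the treatment main effect in the adjusted ordinal regressions, and in interaction models that reuse the same covariates. The unadjusted tests, the interaction terms and, with the dummy as worded, the individual fixed-effects models are not materially affected.

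**What to change.** Delete the MI-provider dummy from the adjusted models. If staff differences are to be controlled, define the variable as the dental staff member who carried out the T0 visit, in both arms. With staff crossed with prisons this leaves the SE ratio at 1.00. With staff fixed to prisons some dummies are redundant (columns/rank 9/6 with one per prison, 13/10 with two) and drop out, but treatment stays identified with ratio 1.00.

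Report provider variation separately, either within the treatment arm or through a treatment-by-T0-staff interaction with centred staff dummies, so that the main effect remains the average effect. Reference coding of that interaction would bring the problem back (SE ratios 1.41, 2.00, 2.39 and 2.83 for 2, 4, 6 and 8 staff, against 1.00 when centred).

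The cost is one sentence in the plan, and no new data if the T0 staff member is already recorded for controls.
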